### ***Health-knowledge and general- and sport-psychological measurements***

By means of questionnaires we will, at baseline, at the end of the stay at DCSH and also 3 and 12 months after end of stay, examine the participants' health, well-being / mental health, ego and task orientation, cohesion of participants, stress levels and sleep habits. During the completion of the questionnaires, there will be a test-responsible present to assist in the possible challenges of reading and understanding the questionnaires. Participants' health-knowledge is measured through a questionnaire (Appendix 2) that examines the participants' learning and understanding of the 11 health messages (Fuller et al. 2010, 2011, 2015, 2016). There is a total of 38 questions. The purpose of the questionnaire is to investigate how much participants have learned in each of the 11 health messages in the program.

Participants' well-being / mental health are measured via PedsQL questionnaire (Varni et al., 1999, Appendix 3), as well as using a Kids Screen questionnaire (Ravens-Sieberer et al., 2001, Appendix 4). The questionnaires aim to measure the well-being of the participants. The scale intends to cover a wide range of dimensions in well-being and contains a total of, respectively, 22 and 25 questions. A previous survey has tested the validity of the questions (Nunnally 1978).

Participants' Ego- and task-orientation is measured through the Task and Ego Orientation Questionnaire (TEOSQ; Duda & Nicholls, 1992). The questionnaire contains 13 questions (7 for assignment and 6 for ego orientation), which can be answered on a Likert scale from 1 to 5, where 1 is "Highly Disagreeable" and 5 is "Fully Agree" (Appendix 5). Task-oriented participants emphasize doing their best, experiencing progress and / or improving skills while ego-oriented participants are measuring themselves against the others and emphasizing to be successful and better than others. The questionnaire is validated and translated into Danish. TEOSQ has been used in studies in Danish studies (Thomas et al., 2016).

Participants' cohesion is measured via the Youth Sport Environment Questionnaire (YSEQ, Eys et al., 2009, Appendix 6). The questionnaire contains 12 questions that can be answered on a Likert scale from 1 to 5, where 1 is "Does not fit" and 5 is "Fits completely". Cohesion describes how the participant perceives the class's solidarity to social aspects and the ability to solve tasks in unity (Carron et al., 2002). The questionnaire is validated in English (Eys et al. 2009) and the Danish version has been used in similar studies (Elbe et al., 2016).

The Children's Sleep Habits Questionnaire (CSHQ) is used in the assessment of the participants' sleep habits. The questionnaire is available in several versions (Appendix 7-8), containing 33 or 26 questions for completing by the parents and the child itself, respectively. The questions are answered "Commonly" (5-7 t. Weekly), "Sometimes" (2-4 t. Weekly) or "Rare" (0-1 t. Weekly). The questionnaires clarify sleep habits, sleep disorders and consequences of disturbed sleep (Owens et al., 2000a). The questionnaires are validated in English (Owens et al., 2000b), and CSHQ - parent version has been used in studies in Danish (Hjort et al., 2014). The children's version will be used at baseline, after the 10week residential stay, as well as both 10 weeks and 12 months after the stay at DCSH, while the parent version will be used at baseline and 10 weeks and 12 months after the stay. The children's version (Appendix 8) is attached in English. Before the start of the project, the version will review a translation process into Danish, back-translation into English, as well as pre-testing with 5-10 children, and can thus be used as a self-reporting version.

Participants' stress levels are measured via the Strengths and Difficulties Questionnaire (SDQ). The self-completion version for the children is validated in English (Goodman et al. 1998). The questionnaire contains 30 questions answered with "fails", "fits partially" or "fits well" within the last 6 months (baseline - afterwards it is within the last month). The student version (Appendix 9a + b) will be used at baseline after the stay, as well as both 10 weeks and 12 months after the stay at DCSH (Obel et al., 2004). The questionnaire reveals symptoms in emotional, behavioral, hyperactivity / concentration and social challenges. The questionnaire for parent completion (Appendix 10a + b) was previously used in studies with Danish youth (5-12 years) (Kristensen et al., 2014, Niclasen et al., 2012). The parent version will be used at baseline and 10 weeks and 12 months after the stay.

### **Other measurements**

In addition to the above test days, the following measurements are performed during the high intensity training in the SG+:

#### ***Continuous intensity measurements during training***

Frequently during the training intervention, activity registrations will be made. There will be measured up to 4 times at approx. 50 participants from both DCSH. Activity registrations include pulse rate measurements (Polar Team 2), GPS measurements and accelerometer measurements to determine

intensity and motion pattern analysis. At the trainings where activity registrations are made, short questionnaires are also provided for measurements of perceived exertion and flow in relation to the training (Elbe et al., 2010, Appendix 11). In relation to accelerometer measurements, there will also be a record of participants' daily activity level and sleep patterns, up to 25% of participants, during the intervention period.

The questionnaires, within the various measurement areas, are based on already tested reliability questionnaires relative to the participant population, cf. the above references. The questionnaires are introduced by a qualified person with relevant professional education, which is also present during the completion of the forms. The answers to the questionnaires are treated confidentially as all other individual results. The participant will not be asked to give up his name and the questionnaires will be coded.

### ***Additional information***

Via a parent-filled questionnaire (Appendix 12) knowledge about socioeconomic data, ethnicity, background information and health surveys are obtained. Absence lists, as well as results from school-related tests, are also obtained through the DCSH in order to utilize the large number of participants in various subgroup analyses.

### **Side effects, risks and disadvantages of the participants**

#### ***Tests and measurements***

Overall, tests and measurements in the study are non-invasive. In relation to the training intervention, football represents an activity that children already do to a large extent in daily life: Children play soccer, running and jumping, etc. Therefore, there are no particular risks considered for these activities. There may, however, be injuries in football training, but the injury rates are low, see section on training protocol.

#### **Biobank**

Hair samples and salivary samples are anonymized and stored for total analysis after completion of the test period. All samples are destroyed after analysis. Hair samples are stored at room temperature, and saliva samples on freezer (initially -20 degrees, then -80 degrees).

### **Scientific ethical statement: Advantages and risks**

Football training for 10 weeks is considered to be a training improvement and generally health-enhancing for recruited participants. More generally, it is a declared goal of the study to contribute with information that can form the basis for recommendations regarding health effects of football training for overweight children at DCSH. In relation to paediatric research, the project will be able to contribute with new knowledge about the effects of a health-enhancing model and this society benefit is estimated to exceed the risks for the children in both the training and the various tests.

All training and tests are carried out by staff with the right professional qualifications. The well-being and safety of the participants will be of highest priority. There will therefore be great attention to the well-being of any specific child in carrying out the protocol's procedures, and the child will be excluded from the study if it is considered to be the best for the child, and subsequently the child and his/her parents will be informed of the basis for the decision. As a participant / parent, knowledge of the state of health in the form of blood pressure and the child's physical ability is given in addition to knowledge of intermittent exercise capacity, balance and spring strength. Compared to all these measurements, participants / parents will be able to see how he or she is relative to the average, so that it can be evaluated whether the child is over, below or in line with the standard. Only participants / parents receive the results of the individual measurements. As for the participants in the DCSH with the standard program, they must follow the standard program, and are, through participation, given test results and other information of personal interest.

### **Personal information**

The study is reported to the Data Inspectorate as a public research project under the Institute's Joint Review System, by journal number 2015-57-0008. Information regarding the participants is protected under the Personal Data Processing Act - Personal Data Act and Health Act. All data will be encoded so that participants' results can only be identified by relevant persons. After the intervention period, each participant will have the opportunity to access own data and average data for the entire group. In the consent statement, parents respond to whether the participants/parents want access to their own data within four months after the end of the project. Information that appears in connection with the research project is subject to confidentiality. By publication in a scientific journal, all data will appear in anonymous form. Both positive, negative and inconclusive results will be published.

Authorities, controlling health science research projects have the right to access data; these authorities will also be subject to professional secrecy. All data will be fully anonymized after the end of the project.

The study is conducted in full compliance with the Helsinki Declaration.

### **Financial aspects**

The project is initiated by [name], Professor of Sport and Health, at the Department of Sport and Biomechanics at the University of Southern Denmark and Honorary Visiting Professor at the University of Exeter, England. The project is funded in collaboration between the University of Southern Denmark and the University of Copenhagen. There are received funds from TrygFonden, Helsefonden and Augustinusfonden for manpower and measuring equipment. All external co-financing will be deposited on a SDU research account subject to public audit. If further support is granted to the project in connection with other applications, the Regional Scientific Ethics Committee will be informed of this and the participant information will be updated with the name of the grantor and the amount of support. The updated participant information will be provided to the participants. There is no one in the project group that is affiliated with private companies or funds with interests in the research project.

### **Remuneration or other benefits**

Compensation for transport costs or loss of earnings for the parents is not compensated because all testing and training takes place at the DCSH or in the participants own home.

### **Recruitment of participants**

The participants are recruited from two DCSH. In the project's cooperation agreement, it is specified that two of the DCSH change practice for one year. In this manner, all the children at the two DCSH are participating in the HIHE intervention, regardless of their participation in tests. To investigate the standard program, all tests will be carried out at both of the DCSH for one year. After the first year the two participating DCSH change intervention group. Alongside the general information about the stay at the DCSH, written information about the study will be provided and subsequently an oral information meeting / parent meeting cf. the description below.

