### Statistic and power calculation

The primary outcome of the project is fat percentage, and among the most important secondary outcomes are aerobic fitness, health-knowledge and well-being. The power calculation is based on the result of the pilot project (Ørntoft et al. 2016). The power calculation is measured with t-test. Some variables are expressed in table below and are based on the development on variables from the pilot study and a study with children from the same age group as on the DCSH (Bendiksen et al. 2014). The calculations are based on a power of 0.80 and p-value of 0.05.

Calculation of number of participants (N) in relation to the evaluation on the DCSH standard program and the assessment of activity and health-program (HIHE).

Power calculation	Intervention group (HIHE)	Standard group	IG vs SG	Delta IG SG Sample size
Fat percentage, intervention period	-9.6 (4.2)	-8.9 (3.7)	-0.6 (2.3)	232
Fat percentage, follow- up period	5.0 (13.4)	8.4 (12.9)	-3.3 (11.2)	182
Aerobic fitness	148 (63)	-106 (83)	254 (85)	4
Health-knowledge	11.9 (23.5)	2.6 (23.7)	9.4 (23.5)	100
Muscle mass	0.6 (0.7)	0.5 (0.9)	0.6 (0.8)	29

Number of participants, 1:1 randomisation	Number of participants with 75% at post-tests
464	580
364	455
8	10
200	250
58	73

The calculations are based upon a randomisation of 1:1, 50% of the participants participate in the standard program. Based on the power calculation, the total number of participants is estimated to be approx. 600 children. This is under the consideration of a completion rate of 75%.

All outcomes will be analyzed by means of linear mixed models including two-way interaction between intervention (standard and intervention) and time (before and after) as fixed effect and child and site as random effects (to account for differences between children and between sites, respectively). Adjustment for age, sex, and possibly other covariates/confounders will also be included as fixed effects in the models.

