## Method

### Design

Approximately 600 boys and girls in the age 7-14 years are recruited from two DCSH. The design is a cross-over design at DCSH level over a two-year period with two intervention groups: A standard group (with the standard program (SG)) and a standard + HIHE (SG+). In SG+ the children will, in addition to the standard program, play recreational football 2x45 min. a week. In SG the children will perform the planned activities according to the schedule. The training in SG+ will be performed indoor or outdoor on grass (depending on the facilities on the specific DCSH) with different football exercises (dribbling, ball control, passes etc.) and small-sided games with high intensity (3v3 to 5v5) on two goals. All training sessions take place on the DCSH or in the immediate vicinity of the DCSH. Every week, a specific football skill is connected with a health message. E.g., the skill of passing the ball to each other is related to respect of each other and avoid bullying.

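### The plan does not say which house runs which program in which year, and the model has no year-by-time term, so year-to-year drift could enter the HIHE contrast wholly or in part

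*Combined protocol and SAP*

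**What the plan says.** Design: "The design is a cross-over design at DCSH level over a two-year period with two intervention groups", namely the standard program (SG) and the standard program plus HIHE (SG+). It does not say which house starts with which.

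Recruitment of participants says that two houses change practice for a year, and continues: "In this manner, all the children at the two DCSH are participating in the HIHE intervention, regardless of their participation in tests". Then: "To investigate the standard program, all tests will be carried out at both of the DCSH for one year". Then: "After the first year the two participating DCSH change intervention group".

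Statistic and power calculation gives one model for all outcomes: "two-way interaction between intervention (standard and intervention) and time (before and after) as fixed effect", with "child and site as random effects". On covariates: "Adjustment for age, sex, and possibly other covariates/confounders will also be included as fixed effects in the models". Year is not named, either as a main effect or by time. The same section refers to 1:1 randomisation, but no section says whether children, houses or the order of programs are randomised.

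**The concern.** The sentences in Recruitment of participants allow two layouts.

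- **Same-year layout.** Both houses run HIHE in one year and the standard program in the other.
- **Swap layout.** In each year one house runs SG+ and the other SG, and they exchange after a year.

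The layout decides whether the HIHE question can be answered at all. The power table assumes that the standard group changes by -8.9 in fat percentage and that HIHE adds -0.6. A contrast that small beside the shared change is sensitive to anything that alters the stay's own effect from one year to the next, such as staffing, intake or testers. Admission is continuous, so each year brings different children. The model's random site effect absorbs differences in level between houses. It does not absorb differences between years in the before-to-after change.

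**Working it through.** **Inputs from the plan** (Statistic and power calculation, unless noted): contrast 0.6 with SD 2.3; standard-group change -8.9; alpha 0.05; power 0.80; t-test; 1:1; about 600 children with 75% completion; 24 to 48 children per house (Participants section).

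**Assumptions, because the documents give no figure:** a year-to-year drift in the stay's effect, common to both houses, of 0.1 to 0.9; house splits of 50:50, 60:40 and 2:1, stable over both years. The 2:1 split is the widest that the 24-to-48 range allows, 48/(48 + 24) = 2/3. That range describes the houses in general, not the two study houses.

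**1. Reproducing the plan's figure.** A two-sided t-test with difference 0.6 and SD 2.3 needs 231.6 per arm, hence the tabled 232. One-sided gives 182 and does not match. I use 0.6 because it reproduces the table, although -9.6 minus -8.9 is -0.7. Completers: 600 × 0.75 = 450, or 225 per arm. SE = 2.3 × √(2/225) = 0.217, and power for 0.6 is about 79%. Like the plan's calculation, this treats children as independent.

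**2. Same-year layout.** For mean changes in the four house-by-year cells, the design matrix with intercept, program and year has rank 2 of 3. Program and year cannot be separated, and drift passes 1:1 into the program estimate. The drift that equals the planned contrast is 0.6/8.9 = 6.7% of the stay's effect. With no true HIHE effect, the two-sided false-positive rate is P(|Z + drift/SE| > 1.96):

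| Drift | Share of 8.9 | False-positive rate |
|---|---|---|
| 0.1 | 1.1% | 7.5% |
| 0.2 | 2.2% | 15% |
| 0.3 | 3.4% | 28% |
| 0.6 | 6.7% | 79% |

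**3. Swap layout, model as stated.** Let house A have share s of the children in both years and run SG+ first. The year-2 share is 1 - s among SG+ children and s among SG children. The bias is therefore drift × (1 - 2s), in size |2s - 1| × drift.

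| Split | Share of drift entering | Bias, drift 0.3 | Bias, drift 0.9 |
|---|---|---|---|
| 50:50 | 0 | 0 | 0 |
| 60:40 | 0.20 | 0.06 | 0.18 |
| 2:1 | 0.33 | 0.10 | 0.30 |

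At 2:1, a drift of 0.3 gives 7.5% false positives and a drift of 0.6 gives 15%.

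**4. Swap layout with year-by-time added.** The term is estimable and the bias from a common drift is zero. The contrast becomes the average of the two within-house differences.

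- Equal houses: SE stays at 0.217.
- 2:1 (cells of 150, 150, 75, 75): variance = 0.25 × 2.3² × (2/150 + 2/75) = 0.0529, so SE = 0.230. The ratio to the unadjusted variance is 0.0529/0.0470 = 1.125. Power for 0.6 falls from about 79% to about 74%.

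Adding house-by-time as well leaves these SEs unchanged.

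**The case against.** The strongest reply is that a swap is the natural meaning of a house-level cross-over in which the houses change group after a year. The other sentences in Recruitment of participants can be read house by house: each house has one year of changed practice and one year of standard-program testing. The remark that all children take part regardless of testing may mean only that HIHE is house-wide, as the Participants section also says. This stands, and it limits what can be claimed. A reader might infer that both houses are definitely on the same program in the same year. The documents do not settle that, and the finding is an ambiguity.

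Three other strong readings are also unsupported.

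- **That the missing year term is what lets a small drift pass for the HIHE effect.** In the same-year layout the term is irrelevant, because no term can help. In the swap layout it matters, but even at 2:1 the drift must reach 0.6/(1/3) = 1.8, about 20% of 8.9, to produce 0.6.
- **That the contrast could come out with the wrong sign.** If the true effect is the planned 0.6, this needs an opposing drift above 0.6 in the same-year layout, or above 1.8 in the swap layout at 2:1. Nothing in the documents points to drift of that size.
- **That drift cancels only with equal houses.** Equal numbers in both years suffice, but the balance depends on all four house-by-year counts.

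The allowance for other covariates leaves room for year but does not commit to it, and a year main effect would adjust levels rather than change. The aim of documenting the effect of the stay itself does not rest on this contrast.

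**Conclusion.** The point holds as an unstated layout plus a missing model term, with different consequences under the two readings. In the same-year layout, SG+ versus SG is a comparison of two calendar years, and a drift of 6.7% in the stay's effect equals the planned contrast. In the swap layout the stated model is unbiased for a common drift when the houses contribute equal numbers in both years. Otherwise, for an assumed drift of 0.3 to 0.9, the bias is 10% to 30% of the planned 0.6 at 60:40 and about 17% to 50% at 2:1. Drift and split are both assumptions, so these figures show sensitivity and do not predict what will happen. The point is more than missing detail: one layout leaves the HIHE effect unidentifiable, and the other has a better analysis available at small cost.

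**What to change.** 1. In Design and in Recruitment of participants, state that in each year one house runs SG+ and the other SG and that they swap after one year. Draw the starting house by lot if feasible. With two houses this gives little balance, but it removes choice from the order.
2. In Statistic and power calculation, prespecify year-by-time as a fixed effect. House-by-time is optional.
3. If both houses must run the same program in the same year, state that SG+ versus SG compares two calendar years and cannot be attributed to HIHE.
4. State as a limitation that house-specific drift between years stays confounded with HIHE even after these changes. With two houses and two years in opposite order, the program contrast is itself the house-by-year interaction.

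The cost is a few sentences and one model term, with the precision cost shown in step 4 of the working: none with equal houses, and about 6% in the SE at 2:1.

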### **Publication of study results**

The intention is to publish scientific articles on the results of the project during 2021-2022, including both the short and long-term effect of the DCSH standard program and the effect of the HIHE program. If it is not possible to publish the results in a journal, the results will be published otherwise. The primary test results will also be published in Danish in 2021, partly as a research report in Danish and partly in short format for use in DCSH setting, both in printed and electronic versions. In addition, the plan is to organize at least two seminars on the DCSH efforts and the local follow-up to the DCSH efforts by 2021. Both positive, negative and inconclusive results will be published. The project is registered at [www.clinicaltrials.gov](http://www.clinicaltrials.gov)

